##### **3.2.2 Eosinophil counts in the blood**

Absolute and percentage changes from baseline Week 0 (Visit 4) in blood eosinophil counts (from hematology) at each post-baseline visit are the secondary efficacy variables.

These variables will also be used to assess the treatment effect over time of eosinophils in the blood.

##### **3.2.3 Pre-bronchodilator forced vital capacity**

The change from baseline (Visit 4) in FVC to each of the post-baseline visits will be a secondary efficacy variable for this study.

##### **3.2.4 Asthma Control Questionnaire-6**

The Asthma Control Questionnaire-6 (ACQ-6) is a shortened version of the ACQ that assesses asthma symptoms (nighttime waking, symptoms on waking, activity limitation, shortness of

breath, wheezing, and short-acting  $\beta_2$  agonist use) omitting the FEV1 measurement from the original ACQ-7 score.

Patients are asked to recall how their asthma has been during the previous week by responding to 1 bronchodilator use question and 5 symptom questions. Questions are weighted equally and scored from 0 (totally controlled) to 6 (severely uncontrolled). The mean ACQ-6 score is the mean of the responses. Mean scores of  $\leq 0.75$  indicate well-controlled asthma, scores between 0.75 and  $< 1.5$  indicate partly controlled asthma, and a score  $\geq 1.5$  indicates not well controlled asthma. Individual changes of at least 0.5 are considered to be clinically meaningful.

The questionnaire will be completed at the study center via provided site tablet (ePRO) in accordance with schedule provided in CSP Section 4, Tables 2 and 3.

The outcome variable for ACQ-6 will be the change in mean score from baseline to each of the post-randomization periods. There will be no imputation for missing values.

Patients will be categorized according to the following limits ([Juniper et al 2005](#)):

- $ACQ-6$  (post-baseline visit – baseline)  $\leq -0.5 \rightarrow$  Improvement
- $-0.5 < ACQ-6$  (post-baseline visit – baseline)  $< 0.5 \rightarrow$  No change
- $ACQ-6$  (post-baseline visit – baseline)  $\geq 0.5 \rightarrow$  Deterioration

An ACQ-6 responder will be defined as a patient who had improvement on ACQ-6, ie, an ACQ-6 responder variable takes value 1 if change from baseline to post-baseline visit in  $ACQ-6 \leq -0.5$  and 0 otherwise.

Furthermore, patients will be categorized according to their ACQ-6-defined asthma control status at the baseline and at each post-baseline visit using the following score thresholds ([Juniper et al 2006](#)):

- $ACQ-6 \leq 0.75 \rightarrow$  Well-controlled
- $0.75 < ACQ-6 < 1.5 \rightarrow$  Partly controlled
- $ACQ-6 \geq 1.5 \rightarrow$  Not well-controlled

In addition to ACQ-6, the ACQ-5 score will be calculated by omitting the question related to rescue medication use. The change in mean score from baseline to each of the post-randomization periods will be calculated and the asthma control responder status will be derived as defined above for ACQ-6. Patients will not be categorized as well-controlled, partly controlled, and not well-controlled based on ACQ-5.

### **3.2.5 St. George's Respiratory Questionnaire**

The St. George's Respiratory Questionnaire (SGRQ) is a 50-item PRO instrument developed to measure the health status of patients with airway obstruction diseases (Jones et al 1991). The questionnaire is divided into 2 parts:

- Part 1 consists of 8 items pertaining to the severity of respiratory symptoms in the preceding 4 weeks;
- Part 2 consists of 42 items related to the daily activity and psychosocial impacts of the individual's respiratory condition.

The SGRQ yields a total score and 3 domain scores (symptoms, activity, and impacts). The total score indicates the impact of disease on overall health status. This total score is expressed as a percentage of overall impairment, in which 100 represents the worst possible health status and 0 indicates the best possible health status. Likewise, the domain scores range from 0 to 100, with higher scores indicative of greater impairment. Specific details on the scoring algorithms are provided by the developer in a user manual (Jones et al 2009).

The change in mean total score in SGRQ from baseline (Visit 4) to each of the post-randomization periods in total score will be a secondary efficacy variable for this study.

For the responder analysis of SGRQ, a responder will be defined as an individual with a  $\geq 4$ -point decrease (improvement) in SGRQ total score from baseline to each post-baseline visit.

### **3.2.6 Fractional exhaled nitric oxide measurement**

The mean change from baseline of fractional exhaled nitric oxide (FeNO) to EOT visit will be a secondary efficacy variable.

Airway inflammation will be evaluated using a standardized single-breath FeNO (ATS 2005) test.

Since spirometry can potentially impact the nitric oxide measurement, the FeNO test needs to be completed prior to spirometry. In addition, patients should not eat or drink 1 hour prior to having the FeNO, as this may affect the results.

While sitting, patients are to inhale to total lung capacity through the NIOX MINO® Airway Inflammation Monitor (Aerocrine, New Providence, New Jersey) and then exhale for 10 seconds at 50 mL/sec (assisted by visual and auditory cues). The value obtained will be recorded and the process will be repeated multiple times. Average of valid replicates provided by the ERT lab will be used in the analysis of the FeNO (ppb) data.

### **3.3 Exploratory efficacy outcome variables**

#### **3.3.1 Patient Global Impression of Severity**

Patient Global Impression of Severity (PGI-S) is a single question asking the patient to rate the severity of their symptoms using a 6-point categorical response scale (0=no symptoms, 6=Very severe symptoms). Improvement from baseline using the PGI-S will include changes from moderate, severe, and very severe to no symptoms, very mild, and mild.

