5.3.2.3 Patient Global Impression of Severity assessments

The Patient Global Impression of Severity (PGI-S) is a single item designed to capture the patient's perception of overall symptom severity at the time of completion using a 6-point categorical response scale (no symptoms to very severe symptoms). For the time of completion, refer to [Table 3](#).

The PGI-S should be completed on the site tablet by the patient before other study assessments and IP administration per the schedule provided in [Table 3](#)

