8.4.1.7 Patient Global Impression of Severity

Patient Global Impression of Severity (PGI-S) is a single question asking the patient to rate the severity of their symptoms using a 6-point categorical response scale (0=no symptoms, 5=very severe symptoms). Improvement using the PGI-S will include changes from moderate, severe, and very severe to no symptoms, very mild, mild as well as patients who have improvements in their responses from baseline.

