#### **4.2.7 Exploratory efficacy outcome variable**

##### **4.2.7.1 Exploratory analysis of PGI-S**

The same analysis approach described in the primary analysis will be performed on the change from baseline in PGI-S at each post-baseline visit. A summary table will be produced showing the number and percentage of patients with improvement from baseline at each post-baseline visit.

Patients with a PGI-S improvement at the EOT visit will be analyzed using a logistic regression model with covariates of treatment and region.

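### SAP 3.3.1 misanchors the six-category PGI-S at 0 and 6 and, without declaring it, omits the protocol clause that counts any improvement in response from baseline

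*SAP*

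**What the plan says.** **Scale.** Protocol 5.3.2.3 describes a "6-point categorical response scale (no symptoms to very severe symptoms"), without codes. Protocol 8.4.1.7 adds them: "0=no symptoms, 5=very severe symptoms". SAP 3.3.1 keeps six points but moves the upper anchor: "using a 6-point categorical response scale (0=no symptoms, 6=Very severe symptoms"). The same SAP paragraph names six categories: none, very mild, mild, moderate, severe and very severe.

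**Improvement.** Protocol 8.4.1.7 counts the shift from the three worse categories to the three better ones, and then adds "as well as patients who have improvements in their responses from baseline". SAP 3.3.1 gives the shift alone: "Improvement from baseline using the PGI-S will include changes from moderate, severe, and very severe to no symptoms, very mild, and mild".

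**Use.** SAP 4.2.7.1 applies the primary repeated-measures approach to the numeric change in PGI-S. It also tabulates improvers at each post-baseline visit and specifies a model for the end of treatment: "Patients with a PGI-S improvement at the EOT visit will be analyzed using a logistic regression model with covariates of treatment and region". Protocol 8.5.2.1 plans the same two kinds of analysis and treats the change score as continuous.

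**Declared changes.** SAP section 6 lists one departure from the protocol, on ECG intervals. The SAP amendment history has no PGI-S entry.

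**The concern.** There are two separate problems.

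The first is the upper anchor. The PGI-S change is analysed as a number, so the codes matter. The SAP's codes do not fit its own category count, and they disagree with the protocol.

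The second is the definition of a responder. The protocol's second clause makes any move to a lower category an improvement. Without it, the only rule the SAP states is a threshold crossing, which is a different and stricter variable. Someone programming from the SAP alone would produce a by-visit table and an end-of-treatment logistic regression for an endpoint other than the one in the protocol, and a reader of SAP section 6 would not learn of it. Under that rule, patients who start at mild or very mild stay in the denominator but cannot be improvers.

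**Working it through.** **1. Codes against categories.** Unit-step codes from 0 to 5 give 5 − 0 + 1 = 6 values, which agrees with the protocol's six points. Codes from 0 to 6 give 6 − 0 + 1 = 7 values, which agrees neither with the six points nor with the six named categories in SAP 3.3.1.

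**2. What a real code of 6 would do.** Suppose the five lower categories are coded 0 to 4 and very severe is coded 6.
- Very severe to severe scores 6 − 4 = 2 points, instead of 5 − 4 = 1.
- Very severe to moderate scores 6 − 3 = 3 points, instead of 5 − 3 = 2.
- Every move into or out of the top category is inflated by one point, and no other move changes.

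If the data are coded 0 to 5 and only the SAP text is wrong, every change score is as the protocol intends.

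**3. Improving moves.** Take the six categories in order. An improving move is any move to a lower category.
- Protocol definition, any lower category: 5 + 4 + 3 + 2 + 1 = 15 moves.
- Shift named in the SAP: 3 starting categories × 3 finishing categories = 9 moves.
- Not named in the SAP: 15 − 9 = 6 moves, and 6/15 = 40% of the possible moves.

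| Baseline category | Improving moves, protocol | Improving moves named in SAP |
|---|---|---|
| Very mild | 1 | 0 |
| Mild | 2 | 0 |
| Moderate | 3 | 3 |
| Severe | 4 | 3 |
| Very severe | 5 | 3 |
| Total | 15 | 9 |

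The six moves not named are very mild to none, mild to none, mild to very mild, severe to moderate, very severe to severe, and very severe to moderate. All nine named moves are among the fifteen, so the SAP rule is a strict subset of the protocol's.

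**4. Can patients start at mild or very mild?** No eligibility criterion uses the PGI-S. Protocol 3.3.1 requires an ACQ score above 0.75 at Visit 4, and SAP 3.2.4 classes scores above 0.75 and below 1.5 as partly controlled. Such baselines are therefore not excluded, but the documents give no baseline PGI-S distribution and no mapping from ACQ-6 to PGI-S.

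**The case against.** **The anchor looks like a slip.** The SAP paragraph itself says six points and names six categories, and both protocol sections agree on six. Responses are captured on a site tablet, so a wrong figure in the SAP text does not recode them. This stands. A reader might infer that both PGI-S analyses, mean change and improvement, must depart from the protocol. For the mean change the documents do not support that, because nothing in them shows a gap in the coded data.

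**The SAP's verb is not exhaustive.** It says improvement will include the shift, which does not say that nothing else counts. The protocol uses the same verb before adding its second clause. This stands in part: the narrower reading is not certain. But the shift is the only rule the SAP gives, and the clause that widened it is absent. At best the variable is undefined beyond the nine moves.

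**A threshold crossing is a legitimate responder definition.** If any lower category counts, the protocol's first clause is redundant, so the sponsor may have meant to tighten the rule. That is a fair choice for an exploratory endpoint, but a changed definition still has to be declared.

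**The affected baselines may be rare.** Entry also requires ACQ-6 of at least 1.5 at Visit 1, at least two exacerbations in the previous 12 months, and recent symptoms, rescue use or awakenings. This limits what can be said about patient numbers. It does not affect the definition.

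**Conclusion.** The point holds in two parts.

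- **Anchor.** The SAP's codes are inconsistent with its own scale and with the protocol. This is probably a misprint, and the continuous analysis is affected only if very severe was actually coded 6.
- **Improvement.** The SAP omits a protocol clause and does not declare it. If the stated rule is taken as the whole rule, the binary variable covers 9 of the 15 improving moves, and a patient at mild or very mild at baseline could not be an improver on it. That limit applies to the binary variable only; a move from mild to none still counts in the change-from-baseline model.

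A reader might take 6 of 15 to mean that 40% of improvements, or of patients, would be lost. The documents do not support this. The figure counts cells in a grid of possible moves, and the share of patients could be much smaller or larger.

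Nor does the point reach the trial's main result. PGI-S is an exploratory objective in SAP 1.1.4 and an other objective in protocol 2.4, and SAP 4.1 makes all p-values outside the primary analysis nominal.

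**What to change.** 1. In SAP 3.3.1, state the scale as 0 to 5, and confirm that the analysis dataset carries those codes.
2. Analyse PGI-S improvement by the protocol definition, meaning any category lower than at baseline, in both the by-visit table and the end-of-treatment logistic regression.
3. If the shift from moderate or worse to mild or better is also wanted, keep it as a separately named variable and list the change in SAP section 6.

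The cost is a few words of SAP text and one derivation. No new data are needed and trial conduct does not change. Protocol 8.1 requires final SAP amendments to be completed before unblinding, so the correction should be made by then.

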#### **3.3.2 Clinician Global Impression of Change and Patient Global Impression of Change**

Clinician Global Impression of Change (CGI-C) and Patient Global Impression of Change (PGI-C) instruments are used for an overall evaluation of response to treatment. The Investigator (clinician) and the patient will be asked to rate the degree of change in the overall asthma status compared to the start of treatment, ie, randomization visit. A 7-point rating scale will be used: 1=Very Much Improved, 2=Much Improved, 3=Minimally Improved, 4=No Changes, 5=Minimally Worse, 6=Much Worse, and 7=Very Much Worse.

The Investigator and the patient will be asked to rate the degree of change in the overall status compared with the randomization visit. There will be no imputation for missing values.

Patients will also be categorized according to the following responses post-baseline, separately for CGI-C and PGI-C:

- Very much improved, much improved, minimally improved → ‘Improved’
- Very much improved, much improved → ‘Much improved’
- Very much improved → ‘Very much improved’

Agreement between CGI-C and PGI-C will be assessed at each visit, where agreement is achieved when both the Investigator and the patient provide the same response (eg, if both the Investigator and the patient indicate a response of 1 (very much improved) at a particular visit, agreement is achieved for that visit). Agreement will also be assessed for categorized responses at each visit.

A responder will be defined for CGI-C and PGI-C separately as anyone with a response of Improved, Much improved, or Very much improved at the EOT visit.

### **3.4 Sub-study efficacy outcome variables**

Additional assessments will be performed for a subset of patients at designated sites, approximately 50 patients in the study, to determine the effect of benralizumab on the time course of change in lung function as assessed through body plethysmography.

The mean change from baseline (Visit 4) to each of the post-randomization visits up to and including the end of treatment visit (Visit 10) will be used as efficacy variables within the

body plethysmography sub-study analysis set. Baseline is defined as the last non-missing value prior to randomization.

### **3.4.1 Primary efficacy variable**

The primary variable for the sub-study is the change from baseline in residual volume (RV).

### **3.4.2 Secondary efficacy variables**

The secondary efficacy variables for the sub-study include the change from baseline in total lung capacity (TLC), ratio of RV/TLC, inspiratory capacity (IC), and functional residual capacity (FRC), vital capacity (VC).

### **3.4.3 Exploratory efficacy variables**

The exploratory variables for the sub-study are change from baseline in Specific airway conductance (SGaw) and Airway resistance (Raw).

## **3.5 Safety outcome variables**

The following safety data will be collected: reported AEs and SAEs, clinical chemistry, hematology, urinalysis, 12-lead electrocardiogram (ECG), physical examination, and vital signs.

All safety measurements will use all available data for analyses, including data from unscheduled visits and repeated measurements.

Change from baseline to each post-treatment timepoint where scheduled assessments were made will be calculated for relevant measurements. AEs will be summarized by means of using descriptive statistics and qualitative summaries.

No safety data will be imputed. The handling of partial/missing dates for AEs and prior/concomitant medications is detailed in [Appendix 8.2](#).

### **3.5.1 Adverse events**

Adverse events experienced by the patients will be collected throughout the entire study and will be coded using the latest version of the Medical Dictionary for Regulatory Activities (MedDRA) per the Data Management Plan.

Adverse event data will be categorized according to their onset date into the following study period:

- Adverse events in the on-study period are defined as those with onset date on or after the day of first dose of study treatment.

If an AE has a missing onset date, then unless the stop date of the AE indicates otherwise, this will be considered an ongoing AE. Similarly, if an AE has a partial onset date, then unless the partial onset date or the stop date indicates otherwise, this will be considered an ongoing AE.

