##### **4.2.9.1 Adverse events**

Adverse events (AEs) will be summarized for the on-study period, as defined in Section 3.5.1. All summaries will be presented by treatment group.

An overall summary table will be produced showing the number and percentage of patients with at least 1 AE in any of the following categories: AEs, serious adverse events (SAEs), AEs with outcome of death, and AEs leading to discontinuation of IP (DAEs). The total number of AEs in the different AE categories in terms of AE counts will also be presented (ie, accounting for multiple occurrences of the same event in a patient).

Adverse events, AEs with outcome of death, and SAEs will be summarized by SOC and PT assigned to the event by MedDRA. For each PT, the number and percentage of patients reporting at least 1 occurrence will be presented (ie, multiple occurrences of an AE for a patient will only be counted once). Adverse events causing discontinuation of the study treatment and SAEs causing discontinuation from the study will also be summarized.

The rate of AEs per person-years at risk, calculated as (number of patients reporting AE)/(total period with patients at risk for AE), will also be reported. The total period at risk for each patient will be defined as the period from first dose of study treatment to the follow-up visit (Week 16). Rates will be expressed in terms of events per 100 patient-years.

A summary of the most common (frequency of  $\geq 5\%$ ) AEs will be presented by PT. Adverse events will be summarized by PT and Investigator's causality assessment (related versus not related) and maximum intensity. If a patient reports multiple occurrences of the same AE within the same study period, the maximum intensity will be taken as the highest recorded maximum intensity (the order being mild, moderate, and severe). Adverse events of injection site reactions (high-level term of administration and injection site) and hypersensitivity (standardized MedDRA query of hypersensitivity) will be summarized by PT. The summary of injection site reactions will be summarized by injection site location and number of IP administrations.

Adverse events related to device malfunction will be listed. All adverse events will be listed.

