## 8.2 Partial dates for adverse events and prior/concomitant medication and medical history

Dates missing the day or both the day and month of the year will adhere to the following conventions in order to classify treatment-emergent AEs and to classify prior/concomitant medications:

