### Adverse events

- The missing day of onset of an AE will be set to:
  - First day of the month that the event occurred, if the onset YYYY-MM is after the YYYY-MM of first study treatment.
  - The day of the first study treatment, if the onset YYYY-MM is the same as YYYY-MM of the first study treatment.
  - The date of informed consent, if the onset YYYY-MM is before the YYYY-MM of the first treatment.
- The missing day of resolution of an AE will be set to:
  - The last day of the month of the occurrence. If the patient died in the same month, then set the imputed date as the death date.
- If the onset date of an AE is missing both the day and month, the onset date will be set to:
  - January 1 of the year of onset, if the onset year is after the year of the first study treatment.
  - The date of the first treatment, if the onset year is the same as the year of the first study treatment
  - The date of informed consent, if the onset year is before the year of the first treatment.
- If the resolution date of an AE or end date of a IP is missing both the day and month, the date will be set to:
  - December 31 of the year of occurrence. If the patient died in the same year, then set the imputed date as the death date.

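### SAP 3.5.1 and Appendix 8.2 conflict on AEs with incomplete onset dates: 8.2 can count an AE that ended in run-in as on-study, and the placement of wholly undated AEs is unclear

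*SAP*

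**What the plan says.** SAP 3.5.1 defines a single AE period: "Adverse events in the on-study period are defined as those with onset date on or after the day of first dose of study treatment". SAP 4.2.9.1 builds the tables on it: "Adverse events (AEs) will be summarized for the on-study period, as defined in Section 3.5.1". The same section also lists all AEs, whatever their period.

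For incomplete onsets, 3.5.1 gives two rules. With no onset date: "unless the stop date of the AE indicates otherwise, this will be considered an ongoing AE". With a partial onset date: "unless the partial onset date or the stop date indicates otherwise, this will be considered an ongoing AE".

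SAP 3.5 refers the handling of partial and missing AE dates to Appendix 8.2, whose scope is narrower: "Dates missing the day or both the day and month of the year will adhere to the following conventions in order to classify treatment-emergent AEs". Its onset rules depend on where the known month or year lies relative to first dose:

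- Same month, day missing: "The day of the first study treatment, if the onset YYYY-MM is the same as YYYY-MM of the first study treatment".
- Same year, day and month missing: "The date of the first treatment, if the onset year is the same as the year of the first study treatment".
- Earlier month: "The date of informed consent, if the onset YYYY-MM is before the YYYY-MM of the first treatment". An earlier year is treated the same way.
- Later month or year: the first day of that month, or 1 January.

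None of these rules refers to the stop date, and none covers an AE onset that is missing altogether.

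**The concern.** AEs are collected from informed consent (Protocol 6.3.1) and the run-in lasts 5 weeks, so AEs that start and end before dosing will exist. Whether one with an incomplete onset enters the tables depends on these rules, and the two places give different instructions. Section 3.5.1 lets a stop date before first dose keep the AE out. Appendix 8.2, followed as written, brings it in. For a wholly missing onset, 3.5.1 offers a resolution status where a period is needed, and 8.2 is silent, so the programmer has to guess.

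At stake is the accuracy of the on-study AE counts and of the rates per 100 patient-years built on them. One record can be visible in a small trial. If all 115 patients in an arm are dosed, one extra patient moves a preferred term from 5/115 = 4.3% to 6/115 = 5.2%, across the 5% level used for the common-AE table.

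**Working it through.** The plan states no figure on this point, so the check is to apply both sets of rules to the same records.

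Assumed dates: consent 13 Feb 2017, first dose 20 Mar 2017 (35 days later, matching the 5-week run-in).

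| Recorded onset | Recorded stop | SAP 3.5.1 (reading *ongoing* as *on-study*) | Appendix 8.2 onset | Result under 8.2 |
|---|---|---|---|---|
| Mar 2017 | 10 Mar 2017 | Not on-study: stop precedes dose | 20 Mar 2017 | On-study, onset 10 days after stop: **conflict** |
| 2017 | 10 Mar 2017 | Not on-study: stop precedes dose | 20 Mar 2017 | On-study: **conflict** |
| Mar 2017 | 5 Apr 2017 or none | On-study | 20 Mar 2017 | On-study: agree |
| Feb 2017 | any | Not on-study | 13 Feb 2017 | Not on-study: agree |
| Apr 2017 | any | On-study | 1 Apr 2017 | On-study: agree |
| none | none, or after dose | On-study, if *ongoing* is a slip | no rule | **Undetermined** |
| none | 10 Mar 2017 | Not on-study | no rule | No date assigned |

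The defect is therefore confined to the same-month and same-year branches with a stop before first dose, plus the missing rule for wholly undated AEs.

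How often could the same-month branch go wrong? Take an AE lasting 5 days that ends before first dose, with onset spread evenly over the run-in. Its onset can fall on any of 31 days (35 to 5 days before dosing). If first dose is on day D of the month, the onsets sharing that month number max(D − 5, 0), so the affected share is max(D − 5, 0)/31.

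- D = 5 or earlier: 0%.
- D = 20: 15/31 = 48%.
- D = 31: 26/31 = 84%.
- Average over all first-dose dates in 2017: the 31-day months contribute 7 × 351, the 30-day months 4 × 325, and February 276, a total of 4,033. Then 4,033/(365 × 31) = 36%.

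This 36% applies only to AEs of that length that ended in run-in and have the onset day missing and a stop date recorded. The 5-day duration, the even spread and the 2017 calendar are assumptions. The documents do not say how many such records to expect.

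**The case against.** The strongest defence is that 3.5.1 already contains the right principle. It introduces its rules as a way of sorting AEs into a study period by onset date. The exceptions make sense only for that purpose: a partial onset date cannot show whether an AE is ongoing, but it can show whether it began before dosing. Read so, undated AEs stay in the tables and the stop date is checked. This stands. A reader might infer that every undated AE is excluded, or that the plan ignores stop dates. The first is one literal reading and not a stated rule; the second is contradicted by 3.5.1.

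Several provisions also limit the problem. Start and stop dates are collected for each AE (Protocol 6.3.3). Patients are asked about health problems since they were last asked (6.3.5), with planned visits at Days −35, −21, −7 and 0, so year-only run-in onsets should be rare. Missing or impossible data are queried (9.4). No AE-duration summary is specified in SAP 4.2.9.1, and time at risk runs from first dose to follow-up, so an onset later than its stop date distorts no planned duration result. The rules are identical in both blinded arms.

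What the defence does not remove is the conflict. SAP 3.5 points to 8.2 for the detail, no precedence is stated, and a program written from 8.2 would omit the stop-date check. Appendix 8.2 does provide for null medication start dates and uses the end date when assigning them, so the corresponding AE provisions look overlooked rather than rejected.

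**Conclusion.** The point holds as an inconsistency with one demonstrable wrong result. Under Appendix 8.2, an AE with a same-month or same-year partial onset and a recorded stop before first dose is dated after its own end and counted as on-study, although 3.5.1 would let the stop date prevent this. Separately, the placement of wholly undated AEs is ambiguous.

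It does not extend to partial onsets generally, since earlier ones go to the consent date and later ones to the start of the known period. Nor is the share of run-in days that fall in the first-dose month an error rate: it includes AEs still present at dosing or without a stop date, for which 3.5.1 and 8.2 agree.

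The size is unknown and probably small. Run-in AEs precede randomised treatment, so misplaced ones should add similar expected counts to both arms. The primary endpoint is untouched. Severity is low; the case for acting rests on the trivial cost.

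**What to change.** In SAP 3.5.1, replace *ongoing* with *on-study* in both places.

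In Appendix 8.2, state for AE onsets:

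- (a) A partial onset in the same month as first dose, or the same year if the month is also missing, is set to the first-dose date only if the stop date is missing or on or after first dose. Otherwise it is set to the later of informed consent and the first day of the known month (or year), and the AE is not on-study.
- (b) A wholly missing onset is set to the first-dose date and the AE is on-study, unless the stop date is before first dose. In that case onset is set to the informed consent date and the AE is not on-study.

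Applied to the example dates, with a stop on 10 March: onset March 2017 becomes 1 March, onset 2017 becomes 13 February, and a wholly missing onset becomes 13 February, all not on-study. A wholly missing onset with no stop date becomes 20 March and on-study. Every case now has one answer.

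The cost is one word changed in two places, two rules added to the appendix, and the matching conditions in the AE date program. No change to data collection is needed.
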